### **6.2.1. Sample size determination**

The main objective of the study is to show that follow-up via the SENTINEL Lymphoma web-application could make it possible to better identify the significant complications occurring between two systematic follow-up consultations with the specialist in patients followed for high-risk lymphoma. relapse than with standard follow-up. The evaluation of the main objective will be carried out over 6 months of follow-up.

This study is based on a pooled triangle test analysis (24, 25, 26). Two groups will be composed, one will be monitored via the web-application, the other will be monitored in a standard way (consultation and imaging).

A 1: 1 randomization will assign the treatment group to the patient. Stratification on center, autologous transplant, PS, relapse and lymphoma type will be performed to ensure the comparability of our two populations at inclusion.

This sequential method will make it possible to evaluate during recruitment the diagnostic efficiency of significant complications outside systematic consultations while controlling the power (risk of accepting our null hypothesis wrongly) and the type I error (risk of rejecting our wrongly null hypothesis). This design allows us to consider stopping the trial as soon as the information gathered is sufficient to conclude. We will be able to conclude that the web-application is diagnostic efficiently or, on the contrary, that it is lacking in interest.

We set the risk of the first species alpha at 5%, the potency at 90%, we envisage that monitoring via the web-application allows us to identify significant complications between two systematic follow-ups in 90% of patients (i.e. 10% of patient presenting an event not identified early) against 60% (i.e. 40% of patient presenting an event not identified early) in the group followed in a standard way (i.e. a difference of 30%).

The early unidentified event is defined:

- in the web application follow up group by the absence of an alert in the following cases:
  - emergency hospitalization,
  - a medical consultation without follow-up with medical prescription (imaging / drug prescription)
  - a significant event at the classic follow-up consultation (very degraded PS, antibiotic therapy, supportive care with consultation, pulmonary embolism, sepsis, severe depression, etc.)
  
- – in the standard group in the following cases:
  - emergency hospitalization, without medical consultation justifying this hospitalization,
  - a significant event at the classic follow-up consultation (very degraded PS, antibiotic therapy, supportive care with consultation, pulmonary embolism, sepsis, severe depression, etc.).

The events diagnosed during the follow-up consultation will be reviewed, in the form of a list (pooled data from the web-application follow-up and standard groups), by the coordinator, who will rule on the significance of the event.

- The hypotheses are written:

H0: The proportion of patients without an undiagnosed event outside the systematic consultation (follow-up visit and systematic imaging) is not different between the two groups.

H1: The proportion of patients without an undiagnosed event excluding systematic consultation (follow-up visit and systematic imaging) is higher with the web-application (by 30%) compared to standard follow-up (90% against 60%).

With 2 scheduled analyzes, it is necessary to include a maximum of 40 patients per group. The analyzes will be carried out every 2x20 patients included (20 in the control group and 20 in the group followed by web-application)

As the inclusions progress, two statistics will be calculated, one reflecting the efficiency and the other the amount of information accumulated. The whole will make it possible to draw a decisional graph, leaving the area thus drawn a conclusion will be possible. If we find ourselves above the zone we will conclude that H0 has been rejected, if we find ourselves below the zone we will conclude with an acceptance of H0 and therefore ineffective monitoring via the web-application.

CONFIDENTIAL

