#### **2.1.2. Primary endpoint**

The primary endpoint is the appearance of a significant complication detected and confirmed by a medical consultation performed outside of standard follow-up.

The significant complications are:

- emergency hospitalization,
- a medical consultation without follow-up with medical prescription (imaging / drug prescription)
- a significant event at the classic follow-up consultation (very degraded PS, antibiotic therapy, supportive care with consultation, pulmonary embolism, sepsis, severe depression, etc.)

We will identify in the web-app group, the absence of alert in the event of complications and in the standard arm, the absence of medical consultation (attending physician) in the event of complications.

Complications diagnosed during the follow-up consultation will be reviewed in the form of a list by the coordinator, who will rule on the significance of the complication.

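### The primary comparison scores the same event by different rules in the two arms, and 2.1.2 and 6.2.1 do not state the same primary endpoint

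*Combined protocol and SAP*

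**What the plan says.** **Section 2.1.2 (Primary endpoint).** "The primary endpoint is the appearance of a significant complication detected and confirmed by a medical consultation performed outside of standard follow-up". One list of three complication types follows for both arms, including significant events found at the classic follow-up visit. The section then sets arm-specific detection routes. With the application, the route is the alert: "We will identify in the web-app group, the absence of alert in the event of complications". Under usual follow-up, where no alert exists, a doctor's visit takes its place: "in the standard arm, the absence of medical consultation (attending physician) in the event of complications".

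**Section 6.2.1 (Sample size determination).** The tested outcome is an early unidentified event.

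- Web arm: "in the web application follow up group by the absence of an alert in the following cases": emergency hospitalisation; "a medical consultation without follow-up with medical prescription (imaging / drug prescription" (the parenthesis closes there); and a significant event at the scheduled visit.
- Standard arm: only "emergency hospitalization, without medical consultation justifying this hospitalization" and "a significant event at the classic follow-up consultation", the latter without any qualifier.

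The null hypothesis concerns "The proportion of patients without an undiagnosed event outside the systematic consultation". The planning rates are 10% failures (web) and 40% (standard), alpha 5%, power 90%, two analyses and at most 40 patients per group. The coordinator reviews a pooled list of visit-diagnosed events and rules on their significance.

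**Section 5.4.** After an alert the investigator reviews the symptom history and calls the patient, and summons the patient only if the doubt is confirmed.

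**The concern.** Some asymmetry is unavoidable, because alerts exist in one arm only and 2.1.2 announces alert versus consultation as the two detection routes. Section 6.2.1 goes further: it also changes the event list and the qualifiers by arm. Two patients with the same clinical course can then be scored differently because of their arm, so part of any observed difference may come from scoring.

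The endpoint also differs between sections. Section 2.1.2 counts a complication that is detected; 6.2.1 counts freedom from one that is not. A patient without any complication is a success under 6.2.1 and has no endpoint event under 2.1.2. Section 2.1.2 is also at odds with itself, since it lists classic-visit events under an endpoint that requires detection outside standard follow-up.

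This is the trial's only powered comparison, with at most 40 patients per arm and a possible stop after 20 per arm, so a few reclassified patients can change the conclusion.

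**Working it through.** **1. The same event under the 6.2.1 rules** (reading a consultation without follow-up as an off-schedule consultation)

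| Situation | Web arm | Standard arm | Can favour |
|---|---|---|---|
| (a) Off-schedule consultation with prescription, no alert | Failure | Not on the list | Standard |
| (b) Emergency hospitalisation after a justifying consultation, no alert | Failure | Not a failure | Standard |
| (c) Significant event at a scheduled visit, identified earlier by that arm's own route | Not a failure (alert) | Failure if read literally; not a failure under 2.1.2 (earlier consultation) | Web |
| (d) Event preceded by an alert that was dismissed after the call | Not excluded from counting as identified | No counterpart | Web |

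For (d), no time window between alert and event is stated, and 6.2.1 does not repeat the confirmation by consultation that 2.1.2 asks for.

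**2. The plan's own figure.** For a triangular test, take log odds ratio ln 6 = 1.792 (40% against 10%), one-sided 2.5% (sidedness is not stated) and 90% power.

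- Corrected effect: 1.792 × 2 × 1.960/(1.960 + 1.282) = 2.167.
- Boundaries: a = (2/2.167) × ln(1/0.05) = 2.765 and c = 2.167/4 = 0.542. The upper line is Z = 2.765 + 0.542V and the lower is Z = −2.765 + 1.625V, each moved inwards by 0.583√(increment in V).
- With two equal looks the lines meet where 0.542V + 0.583√(V/2) = 2.765, so V = 3.651. Total N = 4V/(0.25 × 0.75) = 77.9, or 39 per arm.

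The stated 40 per arm reproduces; the sample size arithmetic is not the problem. Exact binomial enumeration at 20 and then 40 per arm rejects with probability 2.7% at 40%/40% and 86.8% at 40%/10%.

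**3. Illustrations.** The documents give no rate for any of these situations. Every share below is assumed.

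*(c) Which section is followed.* Suppose the 40% was set under the literal 6.2.1 rule, and a share r of those failures would be excused by the 2.1.2 condition. The standard rate is 0.40 × (1 − r); the web rate stays at 10%, since both sections use absence of an alert there.

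- r = 10%: 36% against 10%, power 78%.
- r = 25%: 30% against 10%, power 58%.

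*(d) Chance alerts, no app effect.* Assume 1–5% false alerts per entry, independent of events. The 14-day maximum interval in 5.2 gives 6–7 entries per three months. The share of failures cancelled is s = 1 − (1 − false-alert rate)^entries.

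- 1 − 0.99^6 = 5.9%: web failure 0.40 × 0.941 = 37.7%, rejection 4.1%.
- 1 − 0.95^7 = 30.2%: web failure 0.40 × 0.698 = 27.9%, rejection 18.1%.

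*(a) and (b).* If these add 5 points to a planned web rate that left them out, the comparison is 15% against 40% and power is 67%.

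At one-sided 5% the pattern is the same: rejection at 40%/40% is 4.8%, (c) gives power of 83% and 68%, and (d) gives rejection of 6.8% and 23.5%.

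**The case against.** The strongest reply has four parts.

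- **Scheduled-visit events.** The bullet sits under a definition of events not identified early, and the surrounding text speaks of events diagnosed at the visit. A complication already diagnosed at an earlier consultation is arguably neither. This stands in part: (c) is a conflict with 2.1.2 only when the bullet is read literally. The missing qualifier still leaves the rule open, clearly so where an earlier consultation took place but missed the event.
- **Alerts.** A reader might infer that any stray alert, months earlier, cancels a failure without anyone acting on it. The documents do not support that: 2.1.2 ties the alert to the complication, and 5.4 requires a history check and a call. What remains is that no window is stated and a dismissed alert is not excluded.
- **Detection routes.** Items (a) and (b) partly follow from the arm-specific routes in 2.1.2 and work against the app, so they are conservative for a superiority claim. That is fair as to direction. But the objective in 2.1.1 is better identification between scheduled visits, and a web-arm patient whose complication is found at an off-schedule consultation has met it, yet is scored a failure.
- **Size.** The illustrations rest on assumed rates. This stands. In particular, if the 40% was set under the 2.1.2 condition, following 2.1.2 costs no power.

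The coordinator's pooled review does not answer the point, because it rules on significance and not on whether an event was identified early.

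**Conclusion.** The point holds and should be corrected before the primary analysis. Section 6.2.1 changes the event categories and qualifiers by arm beyond what 2.1.2 announces, and the two sections do not define the same endpoint. Two analysts, each following one section, could score the same patient differently on the primary test. That conclusion rests on the text and needs no assumed rate.

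A reader might go further and infer that the scoring is tilted towards the app. The documents do not support that: (a) and (b) run against the app, (c) and (d) can favour it, and no frequencies are given. Net direction and size are undetermined. The shifts shown above (power from about 87% to 78–58%; false rejection from 2.7% to 4–18%) show only that modest reclassification matters at 40 per arm. They depend on the assumed shares, on a one-sided 2.5% two-look test, on the 40% having been set under the literal rule, and on alerts being independent of events.

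**What to change.** State one patient-level primary endpoint in the same words in 2.1.2 and 6.2.1: the proportion of patients who, over 6 months, have no significant complication that was not identified early. Patients with no complication count as successes.

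- **Failure events, both arms:** an emergency hospitalisation, or a significant event at a scheduled visit, that was not preceded (since the previous scheduled visit) by an off-schedule medical assessment for that complication, whether or not an alert prompted the assessment.
- **Off-schedule consultation with prescription:** counts as early identification in both arms and leaves the web-arm failure list.
- **Alerts:** count only if they led to such an assessment before the event. Keep absence of an alert, including for off-schedule consultations, for the web-arm sensitivity endpoint in 2.2.1.
- **Coordinator review:** judge both significance and the link between assessment and complication, from a list that shows neither arm nor alert status.
- **Planning rates:** re-justify 40% and 10% under this rule, and restate the power if they change.

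The arm-specific sentence in 2.1.2 must be amended as well.

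**Cost.** e-CRF fields in both arms for the date and reason of off-schedule assessments, including those by the attending physician (2.2.2 plans only counts of consultations); a somewhat larger coordinator review; and possibly a substantial modification under 8.6. The question moves from whether the alert fired to whether the complication was identified early, so consultations sought without an alert also earn credit. Stated power may fall: for assumed rates of 35% against 10%, the two-look design has 75%.

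### Emergency hospitalisations and off-schedule consultations with a prescription bypass the significance review, yet without an alert they are primary failures in the web-application arm

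*Combined protocol and SAP*

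**What the plan says.** Section 2.1.2 lists three classes of significant complication: an emergency hospitalisation; "a medical consultation without follow-up with medical prescription (imaging / drug prescription"), which appears to mean a consultation outside scheduled follow-up; and a significant event found at the scheduled visit. The consultation class has no threshold for severity, cause or novelty.

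The ruling on significance covers the third class only. Section 2.1.2 states: "Complications diagnosed during the follow-up consultation will be reviewed in the form of a list by the coordinator". Section 6.2.1 (Sample size determination) repeats this: "The events diagnosed during the follow-up consultation will be reviewed, in the form of a list". It adds that the list pools both groups. No review is described for the other two classes.

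Section 6.2.1 then defines failure, the early unidentified event, separately by arm:

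- **Web arm:** any of the three classes with no alert.
- **Standard arm:** an emergency hospitalisation without a consultation that justified it, or a significant event at the follow-up visit. The off-schedule consultation with prescription is not listed.

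The planned failure rates are "10% of patient presenting an event not identified early) against 60% (i.e. 40% of patient presenting an event not identified early").

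**The concern.** The same clinical fact is treated differently according to where it is recorded. Antibiotic therapy noted at a scheduled visit goes to the coordinator, who may rule it not significant. An antibiotic prescribed between visits needs no ruling, and neither does any other prescription, including the renewal of a long-standing treatment.

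In the web arm this reaches the primary test. Under section 5.4 the application alerts when the patient's answers suggest relapse. A patient who sees a doctor for a renewal would not be expected to give such answers, so the application is rightly silent, and that silence is scored as a missed complication. An emergency hospitalisation for an unrelated cause is handled the same way.

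The same events also enter two secondary counts in section 2.2.1: the total number of complications, and the number of significant complications that the application did not identify. What is at stake is a conclusion that the monitoring is ineffective, drawn partly from events that were not complications.

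**Working it through.** **Inputs from section 6.2.1.** "We set the risk of the first species alpha at 5%, the potency at 90"%; success 90% against 60%; "This study is based on a pooled triangle test analysis"; "With 2 scheduled analyzes, it is necessary to include a maximum of 40 patients per group", with an analysis every 20 + 20 patients. Sidedness is not stated: H0 is worded as no difference, while under H1 success "is higher with the web-application (by 30%) compared to standard follow-up (90% against 60"%).

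**Step 1: the plan's own figure.** The log odds ratio is ln[(0.9 × 0.4)/(0.1 × 0.6)] = ln 6 = 1.792. For a triangular test, θ' = 2·u_α·1.792/(u_α + u_β), a = (2/θ')·ln(1/2α) and c = θ'/4. With two equal looks and the 0.583 discrete correction, the information I per look solves 2cI + 0.583√I = a, and the maximum N is 2I/(0.75 × 0.25/4).

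- α = 0.025 per side: θ' = 2.167, a = 2.765, c = 0.542, I = 1.825, N = 77.9, so 78 against the stated 80.
- α = 0.05 one-sided: θ' = 2.014, a = 2.286, c = 0.504, I = 1.550, N = 66.1.

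The stated 40 per group is reproduced, so the sample-size arithmetic is not in question.

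**Step 2: effect of unreviewed consultations.** Let q be the share of web-arm patients, among those who would otherwise succeed, who have at least one routine consultation with prescription and no alert within 6 months. The documents give no value for q. If these patients are not already inside the planned 10%, web-arm success is 0.9(1 − q).

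- As written, the standard arm stays at 0.6, because this class is not a failure there.
- For comparison, if the same events were scored as failures in both arms, the standard arm would be 0.6(1 − q).

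The two-look test was enumerated exactly at 20 + 20 and 40 + 40. With equal groups of n, Z = (web successes − standard successes)/2. With S total successes, V = S(2n − S)/(8n), and ΔV is the increase in V since the previous look. H0 is rejected if Z ≥ a + cV − 0.583√ΔV and accepted if Z ≤ −a + 3cV + 0.583√ΔV. The boundaries are one-sided 5%.

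| q | Web success | Power as written (standard 60%) | Standard success if scored in both arms | Power if scored in both arms |
|---|---|---|---|---|
| 0 | 90% | 89% | 60% | 89% |
| 2% | 88.2% | 84% | 58.8% | 85% |
| 5% | 85.5% | 74% | 57% | 79% |
| 10% | 81% | 55% | 54% | 69% |
| 20% | 72% | 23% | 48% | 54% |

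With 40 web-arm patients, 36 successes are planned (40 × 0.9). So q = 5% is 1.8 patients and q = 10% is 3.6 patients.

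**Step 3: splitting the loss.** At q = 10% the loss is 89 − 55 = 34 points as written and 89 − 69 = 20 points with equal scoring. The other 14 points come from the asymmetry between the failure lists. In the as-written case H0 is accepted about 45% of the time, which section 6.2.1 would read as ineffective monitoring.

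**Step 4: sensitivity to sidedness.** At 0.025 per side, power is 87% at q = 0. At q = 10% it is 49% as written and 67% with equal scoring.

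**The case against.** **The planned 10% may already include these events.** Section 6.2.1 sets 10% for events not identified early and defines such events to include this consultation class, so 0.9(1 − q) may count them twice. This stands. The figures apply only to consultations beyond those allowed for, and at q = 2% the loss is modest. A reader might infer that the planned 90% cannot be reached; the documents do not show that.

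**The consultation does not count automatically, and it does not dilute.** This also stands. A reader might infer equal noise in both arms. In the primary comparison, however, the class is a failure only in the web arm and only without an alert, so the effect is a bias against the application that overlaps with the arm asymmetry.

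**Reconciling the arms could remove the problem.** Section 2.1.2 makes failure in the standard arm the absence of a consultation. If a consultation were treated as identification in both arms, or the class were dropped from the web list, prescription consultations would stop being failures. The both-arms column above is thus only one possible outcome. But unreviewed hospitalisations would remain, and so would the unfiltered total of complications. Under the wording in section 2.1.2, where the endpoint is a complication detected off schedule, unreviewed consultations could instead count as detections. The direction would change; the need for a filter would not.

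**The headline requirement already filters.** Section 2.1.2 asks for a significant complication confirmed by a consultation. That does not help with this class, because the consultation with prescription is itself the listed event.

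**The breadth is deliberate.** Sections 1.5.3 and 3.1 aim at any other event that calls for medical treatment. This stands against a rule excluding everything unrelated to the lymphoma. It does not justify counting a renewal with no new problem.

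**Sensitivity.** A reader might infer that the application's sensitivity is necessarily distorted. Section 2.2.2 bases it on imaging results, while section 2.2.1 ties it to the count of complications not identified, so this depends on which text governs.

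**Conclusion.** The gap is in the text. Two of the three event classes carry no significance ruling, and both are web-arm failures whenever there is no alert. Followed literally, correct silence of the application can be scored as a missed complication, which biases the primary comparison against it and inflates the two complication counts in section 2.2.1.

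The size is conditional on three assumptions: the value of q, that the planned 10% does not already contain these patients, and one-sided 5% testing. On those terms the loss is about 5 points of power at q = 2% (89 to 84), 15 at 5% (89 to 74) and 34 at 10% (89 to 55), of which 14 at q = 10% belong to the arm asymmetry. The planned 40 per group is not shown to be wrong. The change should be made before the first 20 + 20 analysis.

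**What to change.** In sections 2.1.2 and 6.2.1 (Sample size determination), state that all three event classes from both arms go to the pooled list, without arm or alert status shown. The list is already described as pooled; masking is not stated. The coordinator rules on every entry by one written significance criterion, fixed before the first 20 + 20 analysis and consistent with the stated aim of events requiring medical treatment. At minimum, the criterion should say that a renewal of ongoing treatment with no new medical problem is not significant. Going further and excluding all problems unrelated to the lymphoma would narrow the stated aim; if the sponsor wants that, it should be declared as a change of endpoint.

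In the same amendment, reconcile the arm-specific failure lists in sections 2.1.2 and 6.2.1, because the effect of the review depends on which events count as failures in each arm. State also whether the planned 10% and 40% refer to reviewed events.

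Cost: revised wording in two sections, preparation of masked entries, a longer list and more judgement calls for the existing reviewer. The last is a real cost, since one person would then rule on every primary event. Masking and a written criterion limit it.

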### **7.2.2. Independent data monitoring committee**

As the patients were not exposed to any additional risk, it was therefore not considered necessary to use an independent monitoring committee in the context of this study.

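### The plan does not say that the coordinator's ruling on events found at follow-up visits is masked to arm and alert status, so part of the primary endpoint is open to bias in either direction

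*Combined protocol and SAP*

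**What the plan says.** - **Who rules, and on what.** Section 2.1.2 (Primary endpoint): "Complications diagnosed during the follow-up consultation will be reviewed in the form of a list by the coordinator". Section 6.2.1 (Sample size determination) repeats the rule, adds that the list combines data from both groups, and again has the events ruled on "by the coordinator, who will rule on the significance of the event". Both sections confine the review to events diagnosed at the follow-up consultation.
- **What counts as significant.** Both sections give examples rather than criteria. They range from pulmonary embolism and sepsis to a course of antibiotics or a supportive-care referral, and the list ends in etc.
- **How the ruling enters the endpoint.** Under Section 6.2.1, a significant event at a follow-up consultation is a failure in the standard arm. In the web arm it is a failure if there was no alert.
- **What else is a failure.** Emergency hospitalisation counts in both arms (in the standard arm, when no consultation led to it). An unscheduled consultation with a prescription counts in the web arm only. Neither is named as going to the coordinator.
- **Masking.** Section 6.2.3 displays the allocated group on the e-CRF, and Section 5.4 sends alerts to the investigator. No section says that arm, alert history or centre is removed from the list, or that the ruling comes before alert status is known. No section withholds the result of the first comparative analysis from the coordinator.

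**The concern.** One person applies an undefined threshold to events that help decide the primary outcome. If that person can see the arm or the alert record, a borderline event may be judged differently in the two groups. In the web arm the link is direct: once it is known that no alert was raised, calling the event significant makes the patient a failure of the application. Knowledge of the first comparative result could have the same effect on later rulings. Section 6.2.1 presents the sequential test as controlling both error rates, but the boundaries cannot protect against outcomes classified differently by arm.

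**Working it through.** **1. Inputs, all from Section 6.2.1 (Sample size determination).**
- Error rates, in per cent: "We set the risk of the first species alpha at 5%, the potency at 90". Sidedness is not stated, so both readings are carried.
- Web arm: 90% success, 10% failure.
- Standard arm: "against 60% (i.e. 40% of patient presenting an event not identified early) in the group followed in a standard way".
- Allocation: "A 1: 1 randomization will assign the treatment group to the patient". There are two analyses, at 20 and 40 patients per group.

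**2. The plan's own sample size.** The usual two-proportion formula, two-sided 5%, 90% power, mean success 0.75:

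n = [1.960 × √(2 × 0.75 × 0.25) + 1.282 × √(0.9 × 0.1 + 0.6 × 0.4)]² / 0.30² = (1.200 + 0.736)² / 0.09 ≈ 41.7, so 42 per group.

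For a triangular test the effect is θ = ln[(0.9 × 0.4)/(0.1 × 0.6)] = ln 6 = 1.792. With two looks and the usual correction for discrete looks, the maximum is 38.9 per group at one-sided 2.5% and 33.1 at one-sided 5%. The stated maximum of 40 therefore reproduces and fits the one-sided 2.5% reading better. This point disputes no figure in the plan.

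**3. Boundaries used for the scenario.** The plan prints none, so standard ones are assumed: reject when Z ≥ a + cV and accept when Z ≤ −a + 3cV, each moved inwards for discrete looks. Z is half the difference in the number of successes; V is the usual information for a 2×2 table. With θ rescaled for unequal α and β, a = 2.765 and c = 0.542 at one-sided 2.5%, and a = 2.286 and c = 0.504 at one-sided 5%.

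**4. Bias model.** There is no true difference, and true failure is 40% in both arms. Let f be the share of web-arm failures that rest on visit-diagnosed events, and d the extra share of those ruled not significant compared with the standard arm. Then x = f × d, and apparent web success = 1 − 0.4 × (1 − x), against 0.60.

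**5. Results** (exact enumeration of both looks):

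| x | Web success | Standard success | False-positive rate, one-sided 2.5% | One-sided 5% |
|---|---|---|---|---|
| 0 | 0.60 | 0.60 | 2.7% | 4.8% |
| 5% | 0.62 | 0.60 | 3.9% | 6.5% |
| 10% | 0.64 | 0.60 | 5.4% | 8.6% |
| 20% | 0.68 | 0.60 | 10.2% | 14.5% |
| 10%, opposite lean | 0.60 | 0.64 | 1.3% | 2.6% |

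With 40 × 0.4 = 16 expected web-arm failures, x = 10% means 1.6 patients reclassified.

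**6. Dependence on f.** For d = 10, 20 and 30%:

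| f | x | One-sided 2.5% | One-sided 5% |
|---|---|---|---|
| 50% | 5, 10, 15% | 3.9, 5.4, 7.5% | 6.5, 8.6, 11.2% |
| 25% | 2.5, 5, 7.5% | 3.3, 3.9, 4.6% | 5.6, 6.5, 7.5% |

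**7. Dependence on the failure rate.** With 25% failure in both arms and x = 20%, the rate is 7.5% instead of 2.8% (one-sided 2.5%), or 13.1% instead of 5.7% (one-sided 5%).

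**8. What equal errors do.** If masking makes downgrading equal in both arms, at 10 to 30% of failures, the false-positive rate stays near nominal: 5.0 to 5.6% for the triangular test at one-sided 5%, and 2.4 to 2.5% for a fixed z-test at one-sided 2.5%. Equal errors still cost power. For a fixed z-test of 60% against 90%, power runs from 92% down to 83% (one-sided 5%) or from 86% down to 74% (two-sided 5%) as the downgraded share goes from 10 to 30%. Masking alone does not prevent that loss, so significance criteria are needed too.

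**The case against.** **Pooling may be meant as the safeguard.** A list combining both groups suggests that arm-neutral review was intended. That is a fair reading, and it rules out saying that the review is unmasked; the documents support only that masking is not specified. Pooling itself does not hide which arm an entry came from, and Section 2.1.2 does not mention it.

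**The coordinator does not decide the whole endpoint.** A reader might infer that every primary-endpoint event passes through this ruling. It does not: only visit-diagnosed events do, and Section 1.3 has the symptom reports analysed by software. A patient who also had an unflagged emergency hospitalisation remains a failure whatever the coordinator decides. This stands and caps the bias. Scenarios that downgrade a share of all web-arm failures assume f = 100%, which the documents do not support.

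**The direction is unknown.** A reader might infer a bias in favour of the application. Nothing shows which way the coordinator would lean. The written failure definitions contain one asymmetry against the application, since the consultation with a prescription counts as a failure only in that arm. This also stands.

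**The missing committee is not evidence.** Section 7.2.2 might be read as refusing independent adjudication. It concerns a monitoring committee, declined because patients face no added risk, and says nothing about ruling on endpoints.

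**Conclusion.** The point holds as an inexpensive improvement. In an open-label trial, one coordinator judges an open-ended class of events that decides part of the primary outcome, and the plan does not state that arm or alert status is hidden. Bias in either direction is possible.

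The size is a scenario, not an estimate. At x between 5 and 20%, the false-positive rate is 3.9 to 10.2% instead of 2.7%, or 6.5 to 14.5% instead of 4.8%; a 10% lean the other way gives 1.3% or 2.6%. These figures rest on standard triangular boundaries that the plan does not print, on 40% true failure in both arms, and on a value of x of which the documents give neither component. They do not show that the trial's error rate is inflated. They show that reclassifying fewer than two of 16 expected failures is enough to move it materially.

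**What to change.** In Sections 2.1.2 and 6.2.1 (Sample size determination), add a paragraph stating that:

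1. Data management produces the pooled list in random order, without arm, alert history, application entries or centre. Where possible it also removes details that reveal the arm, such as whether imaging was scheduled or triggered by an alert (the imaging schedules in Section 5.3 differ by arm).
2. Criteria for a significant event are fixed in writing before the first review, replacing the open-ended examples.
3. Each ruling is locked before it is linked to arm, to alert status or, in the standard arm, to whether a consultation took place.
4. After the first analysis the coordinator is told only to continue or to stop until the remaining rulings are locked.

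A second or independent assessor would strengthen this but is optional.

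The cost is one paragraph, a masked e-CRF listing and a small data-management effort, with no extra patients or visits. Masking will be incomplete, because unmasked investigators record the visit events in the first place; the report should say so. If the list is already masked in practice, writing that down costs almost nothing.
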